4.5.1. Impact of COVID-19 Pandemic

The emergence of the coronavirus disease 2019 (COVID-19) during the conduct of study and the related travel restrictions and quarantines resulted in some subjects experiencing missed infusions, missed assessments, delayed visits, and early withdrawals. These could potentially alter the subject's response to treatment, confound the assessment of the 6MWD and FVC, and impact the analyses.

Assessment and infusion visits that were missed due to COVID-19 related reasons were to be recorded as protocol deviations in the electronic data capture (EDC) and the reasons attributed to COVID-19. Infusions that were missed near the scheduled assessments visits at Weeks 26, 38, and 52 were to be examined on a case-by-case basis to determine whether catch-up infusions were needed, and if so, how many catch-up infusions were needed, prior to rescheduling the visits to perform make-up assessments. As a result, subjects who missed visits due to COVID-19 related reasons could be enrolled longer than 12 months in the study due to delayed visits.

As a general rule, a subject missing at least 2 consecutive infusions just prior to the Week 52 assessments (or between Week 38 and Week 52) due to COVID-19 was required to receive make-up infusions prior to the EOS assessments. The make-up infusions required 4 consecutive infusions to be administered regardless of the number of infusions missed. For example: if a subject missed 3 consecutive infusions at Week 42, 44 and 46, then the subject was required to receive make-up infusions at Week 48, 50, 52 and 54, and the EOS assessments were to be conducted thereafter, prior to Week 56. A subject missing 5 consecutive infusions was to be withdrawn from the study.

Analyses will be performed to assess whether the number of subjects with missing data due to COVID-related reasons are comparable between the 2 groups (at Week 52 and across the study).

5. INTERIM ANALYSES

There is no interim analysis planned for this study.

6. GENERAL CONSIDERATIONS FOR DATA ANALYSES AND HANDLING

6.1. Analysis Populations

The total number of subjects screened, number who screen-failed, and the number randomized (including subjects randomized after rescreening) will be tabulated.

6.1.1. Screen Failures

Subjects who signed an informed consent form (ICF) but failed to qualify for the study and were therefore not randomized, will be considered screen failures.

Information on screen failures will be presented in a data listing.

6.1.2. Safety Population

The safety population is defined as all subjects who received at least 1 dose of study drug (ATB200/AT2221 or alglucosidase alfa/placebo). This population will be used in the assessment and reporting of safety data. Subjects will be analyzed according to the actual treatment received.

6.1.3. All Randomized Population

The 'All Randomized' population consists of all subjects who were randomized, regardless of whether they took a dose of study drug. This population will be used only for subject accounting purposes, and it will be analyzed according to the planned treatment groups.

6.1.4. ITT Population

The intent-to-treat (ITT) population consists of all randomized subjects who received at least 1 dose of study drug. This population will be analyzed according to the planned treatment groups. The ITT population will be used for additional baseline and demographic summaries.

For the purpose of efficacy analysis, the ITT population has been characterized in 2 different ways (ITT-observed [OBS] and ITT-last observation carried forward [LOCF]) (see Section 8.2 and Section 6.3.2 for further descriptions).

6.1.4.1. ITT-OBS

The ITT-OBS is the ITT population using all available, observed data without imputation for missing post-baseline data. That is, missing data at Week 52 and at other visits are not replaced.

The ITT-OBS population is identical to the ITT population as defined above. The mixed-effect model for repeated measures (MMRM) analysis will be performed on the ITT-OBS population.

6.1.4.2. ITT-LOCF

The ITT-LOCF is the ITT population with missing data replaced with the last available value from post-baseline results. That is, the LOCF replaces missing data at Weeks 26, 38, and 52 with the last available endpoint value. Where applicable, the observed baseline result will be used to replace a missing post-baseline result at the Week 12 visit. Imputed baseline value cannot be used to replace missing Week 12 result. The missing value at Week 52 is replaced with the last

available value from the subject in the study. This can be the value from the early termination (ET)/end of study (EOS) visit if available. If not available, the last available value from prior post-baseline visits (Week 38, Week 26, or Week 12, whichever is available) will be used to replace the missing value at Week 52.

Example for visits earlier than Week 52: Suppose the subject only missed the assessment at Week 12 but had assessments at some other visits after Week 12 (ie, Week 26 and/or Week 38 and/or Week 52). Then the missing assessment at Week 12 is replaced with the last available value on/prior to Week 12 (eg, the observed baseline value). If the subject missed the Week 12 visit due to discontinuation/withdrawal from the study and had follow-up assessments at the ET/EOS visit, then the last available value from the ET/EOS visit will be used to replace the missing Week 12 value. This EOS value is then carried forward to replace missing values at Weeks 26, 38, and 52 as the subject had withdrawn from the study since Week 12.

Note: The observed baseline result can only be used to replace missing data at Week 12, where applicable (ie, if the subject has other post-baseline data). It will not be carried forward to replace missing values at Week 26, 36 or 52. In addition, imputed baseline values cannot be used to replace missing post-baseline values.

6.1.5. Modified ITT Population

The modified intent-to-treat (mITT) population is a subset of the ITT population consisting of all randomized subjects who took at least 1 dose of study drug and have both baseline and at least 1 post-baseline assessment for the 6MWD. This population will be analyzed according to the planned treatment groups. The mITT population will be used for subject accounting purposes.

6.1.6. Per-protocol Population

The per-protocol population (PP) is a subset of the mITT population consisting of any mITT subjects who do not have pre-specified protocol deviations that are considered important, as they potentially may have altered the subject's response to study treatment or confounded the study assessments, thereby impacting the analyses of the primary endpoint (6MWD) and the FVC. This population will be analyzed according to the actual treatment received.

The PP population will be characterized separately for sensitivity analyses for the 6MWD and % predicted FVC. The per-protocol population 1 (PP1) will be used for the sensitivity analyses of the 6MWD, while per-protocol population 2 (PP2) will be used for sensitivity analyses of the % predicted FVC.

Pre-specified important protocol deviations leading to exclusion from the PP1 and PP2 populations include those in [Table 2](#). These populations will be determined and finalized before locking the database.

Table 2: Pre-specified Important Protocol Deviations Leading to Exclusion from Per-protocol Populations (PP1 and PP2)

Item	Important Protocol Deviation Description (Excluded from PP1: for 6MWD)	Important Protocol Deviation Description (Excluded from PP2: for FVC)
1.	Subject did not have sufficient treatment exposure (ie, subject did not have at least 80% compliance with study treatment)	Subject did not have sufficient treatment exposure (ie, subject did not have at least 80% compliance with study treatment)
2.	Subject did not have the primary endpoint (6MWD) assessment at the Week 52 visit (including catch-up assessment or delayed visit) due to COVID-19 pandemic or other reasons	Subject did not have FVC assessment at the Week 52 visit (including catch-up assessment or delayed visit) due to COVID-19 pandemic or other reasons
3.	Subject was discontinued from the study for missing at least 5 infusions	Subject was discontinued from the study for missing at least 5 infusions
4.	Subject withdrew consent and/or discontinued from the study	Subject withdrew consent and/or discontinued from the study
5.	Subject was unblinded (accidentally or otherwise) before database lock	Subject was unblinded (accidentally or otherwise) before database lock
6.	Subject was inconsistent in the use/non-use of assisted devices during 6MWT	

Abbreviations: 6MWD = 6-minute walk distance; 6MWT = 6-minute walk test; FVC = forced vital capacity; PP1 = per-protocol population 1 is used for the sensitivity analyses of the 6MWD; PP2 = per-protocol population 2 (PP2) is used for the sensitivity analyses of the percent predicted FVC

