15.3.1. Analysis Populations

Safety Population: The safety population is defined as all subjects who receive at least 1 dose of study drug (ATB200/AT2221 or alglucosidase alfa/placebo). This population will be used in the assessment and reporting of safety data, and subjects will be analyzed according to the actual treatment received.

Intent-to-Treat Population: The intent-to-treat (ITT) population consists of all randomized subjects (regardless of whether they took a dose of study drug). This population will be analyzed according to the planned treatment groups. The ITT population is the primary population for efficacy analyses.

Modified Intent-to-Treat Population: The modified intent-to-treat (mITT) population consists of all randomized subjects who took at least 1 dose of study drug and have both a 6MWD baseline (ie, average of 2 screening 6MWD values) and at least one post-baseline 6MWD. This population will be analyzed according to the planned treatment groups. The mITT population will be used for supportive/sensitivity analyses of the primary and key secondary efficacy endpoints, as well as for baseline and demographic summaries.

Per-Protocol Population: The per-protocol population is a subset of the ITT population that consists of subjects who have no major protocol or site deviations that impact the analyses of the primary endpoints or the integrity of the study, and took only the study drug to which they were randomized. This population will be analyzed according to the planned treatment groups. The per-protocol population may be used in supportive/sensitivity analyses of the primary and/or key secondary endpoints.

Pharmacokinetic population(s) will be described in a separate modeling and simulation plan.

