4.3. Sample Size and Power Considerations

The primary endpoint for this study is the change from baseline to Week 52 in the 6MWD.

Using a 2-group t-test with a 1-sided significance level of 0.025 and a 2:1 randomization ratio, a total of 99 subjects (66 subjects in the ATB200/AT2221 group and 33 subjects in the alglucosidase alfa/placebo group) would yield approximately 90% power to detect a clinically meaningful standardized effect size of 0.7 between the 2 groups in a superiority test for the primary endpoint. This calculation was performed using nQuery 8[®].

Assuming a 10% dropout rate (after randomization), a total of approximately 110 subjects were planned to be randomized to ensure 99 evaluable patients.

Details of the sample size justification are described in [Appendix 1](#).

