7.7. Handling the Use of Assistive Device During the 6MWT

Subjects using a permitted assistive device during the Screening/Baseline 6MWT should use the same assistive device for all follow-up 6MWT assessments in the study. If the subject added a new device, changed the device at certain visits, or did not use the assistive device, then that will be considered a protocol deviation as the change can affect the primary endpoint and the results of these assessments. See Section 6.1.6 and Section 6.4 for the listing of pre-defined major protocol deviations and the listing of intercurrent events.

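### Minor: three per-protocol rules in SAP 6.1.6 need rewording (wrong drug received, changed walking aid, unblinding after the last assessment)

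*SAP*

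**What the plan says.** SAP 6.1.6 takes the per-protocol population as a subset of the mITT set, without pre-specified deviations that could have changed the response to treatment or distorted the assessments. PP1 serves 6MWD and PP2 serves % predicted FVC. Table 2 lists the exclusions. Three provisions matter here.

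- **Treatment received.** SAP 6.1.6 states: "This population will be analyzed according to the actual treatment received". Table 2 has no item for a subject given the wrong drug. Protocol 15.3.1 requires that per-protocol subjects "took only the study drug to which they were randomized", and it analyses them in their planned groups. SAP section 2 says that the final SAP overrides the protocol on analysis.
- **Walking aid (Table 2 item 6, PP1 only).** "Subject was inconsistent in the use/non-use of assisted devices during 6MWT". SAP 7.7 describes the device deviation more widely: "If the subject added a new device, changed the device at certain visits, or did not use the assistive device". It says that such a change can affect the primary endpoint, and it refers to 6.1.6 for the listing. Protocol 12.3.20 asks a subject who uses a device at screening to keep to that device at later visits.
- **Unblinding (Table 2 item 5, both sets).** "Subject was unblinded (accidentally or otherwise) before database lock".

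PP1 and PP2 are used in row 3 of SAP Table 7, an ANCOVA listed among six rows of sensitivity analyses.

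**The concern.** A per-protocol analysis is useful if it removes assessments that a deviation may have spoiled and keeps the rest. SAP 6.1.6 sets that standard itself, and three of its rules do not fully meet it.

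On drug received, the SAP reverses both halves of the protocol's rule, membership and grouping, and gives no reason. A misdosed subject could be carried into the other arm, so the comparison would no longer be between randomized groups. On walking aids, the one device item is narrower than the section that refers to it. On unblinding, the cut-off falls after the point at which knowledge of treatment could influence a subject's own data.

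At stake is the reading of one supporting analysis for 6MWD and one for FVC. If either disagreed with the main result, it would be hard to tell whether the trial or the definition of the set was the cause.

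**Working it through.** **1. The plan's own figure.** SAP 4.3 states the design: "Using a 2-group t-test with a 1-sided significance level of 0.025 and a 2:1 randomization ratio", "66 subjects in the ATB200/AT2221 group and 33 subjects in the alglucosidase alfa/placebo group", and about "90% power to detect a clinically meaningful standardized effect size of 0.7". The noncentrality is 0.7 / √(1/66 + 1/33) = 0.7 / 0.2132 = 3.28. With 97 degrees of freedom the noncentral t gives power 0.902 (normal approximation 0.907). With 10% dropout, 99 / 0.9 = 110. The stated figures reproduce, and nothing below changes them.

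**2. The rules side by side.**

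| Case | Standard in the documents | SAP Table 2 read literally |
|---|---|---|
| Fully dosed with the wrong drug | Protocol 15.3.1: not per-protocol; planned groups | No item; stays in, grouped by drug received |
| One walking aid replaced by another | SAP 7.7: a deviation that can affect 6MWD | A device is used at both visits, so item 6 does not apply |
| Aid started by a non-user, or stopped by a user | SAP 7.7: a deviation | Excluded from PP1 by item 6 |
| Unblinded after the last efficacy assessment, before lock | SAP 6.1.6: exclude if response or assessment may be affected | Excluded by item 5 |

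*Wrong drug.* The case was foreseen: SAP Table 5 lists an incorrect treatment assignment as an intercurrent event. Item 1 (80% compliance) does not clearly catch it. SAP 9.4.2 computes compliance as infusions given over infusions planned, or mg given over mg planned. Both enzymes are dosed at 20 mg/kg (SAP 4.2), so a subject given every infusion of the wrong enzyme could score 100%. The SAP does not say whether such an infusion counts, nor what the actual treatment is for a subject who received both drugs. The parent mITT set is analysed by planned group (SAP 6.1.5).

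*Unblinding.* Protocol 8.4 places the final analysis after all subjects have completed or withdrawn. An early completer therefore has an interval between last assessment and lock. Unblinding in that interval cannot change a walk or an FVC already recorded.

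**3. Yardsticks on assumed counts.** The documents give no counts. Power at effect size 0.7 is used only as a scale, because PP1 carries no power claim.

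- Losing 3, 6, 9 or 12 subjects in 2:1 proportion: power 0.893, 0.883, 0.872 or 0.861, against 0.902.
- Control subjects who received the new treatment throughout:

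| Number | Excluded (66 vs 33 − m) | By drug received (66 + m vs 33 − m) |
|---|---|---|
| 1 | 0.896 | 0.897 |
| 2 | 0.889 | 0.892 |
| 3 | 0.882 | 0.887 |

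The two treatments of such subjects differ by at most 0.005 in power. The reason to prefer exclusion is the integrity of the comparison.

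- Three controls who change device and each gain an assumed 40 m: 3 × 40 / 33 = 3.6 m on the control mean, or 3.6 / 20 = 18% of the 20 m that protocol 6.5 regards as important. Six such subjects in the larger arm give 6 × 40 / 66 = 3.6 m, so equal rates cancel.
- Three controls dropped only for late unblinding: √(1/66 + 1/30) / √(1/66 + 1/33) = 0.2202 / 0.2132 = 1.033, a 3.3% larger standard error.

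**The case against.** The strongest reply is that little depends on these rules. PP1 and PP2 feed one row of sensitivity analyses and take no part in the testing hierarchy of SAP 8.4. That stands, and it sets the grade.

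On drug received, the SAP overrides the protocol by its own terms, grouping by drug received is a known per-protocol convention, and Table 2 is introduced in words that do not make it exhaustive. All true. But no other pre-specified list exists, and a convention does not explain why a stated rule was reversed.

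On walking aids, item 6 is the only device entry in the section to which SAP 7.7 refers, so it can fairly be read as shorthand for 7.7. A reader might infer that changed devices are certainly kept in PP1. The documents support only a gap in the literal wording. A reader might also call it an error that item 6 applies at every visit when the endpoint is Week 52. It is not: protocol 12.3.20 requires the same device at all later visits, so the wider rule is consistent with it.

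On unblinding, a lock-date cut-off is a simple line that at worst excludes too many. A reader might infer that completers are routinely unblinded when they enter the extension study. The documents do not say so. The extension is optional, everyone in it receives ATB200/AT2221 and entry does not reveal the earlier arm. No lock date is given. The routes to individual unblinding that the protocol describes are narrow (emergency in 11.6.3, pregnancy in 13.4). So the number affected may be nil, although the cut-off still does not match the SAP's stated reason for exclusion.

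**Conclusion.** The point holds as a minor one. The clear conflict is on drug received: protocol 15.3.1 and SAP 6.1.6 give opposite rules for membership and grouping, and the SAP does not explain the change. The walking-aid item needs aligning with SAP 7.7. The unblinding item excludes more than the SAP's own criterion supports.

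The size is unknown and probably small, since every count used above is assumed. The claim rests on the wording alone: a literal reading of item 6, and compliance formulas that do not say how a wrong-drug infusion is counted.

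A reader might go further and conclude that the per-protocol sets select the wrong subjects in general, or that the efficacy conclusion is at risk. The documents do not support either. The primary MMRM on ITT-OBS keeps the observed walks of subjects with such deviations under its treatment-policy strategy, and the alpha control does not use PP1 or PP2.

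**What to change.** Make three wording changes in SAP 6.1.6 before the populations are finalized and the database is locked.

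1. Add a Table 2 item for PP1 and PP2: *subject received any study drug other than the one randomized*. Analyse both sets by randomized group, as protocol 15.3.1 states.
2. Reword item 6 to match SAP 7.7: *an assistive device was added, changed or not used relative to the baseline 6MWT*. Whether to apply it at all visits or only at Week 52 is the sponsor's choice and should be stated.
3. Reword item 5: *subject was unblinded before the subject's Week 52/ET efficacy assessment*, counting a delayed or make-up assessment as that assessment.

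The cost is SAP text and a re-run of the set definitions; PP1 and PP2 membership may change by a few subjects. Protocol 12.3.3 records ambulatory aids, and 11.6.3 requires premature unblinding to be documented. Neither shows that the device used at each 6MWT is captured, nor that unblinding is dated, so both should be confirmed before the items are reworded.

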6.1.7. Completers

The Completers population consists of subjects who completed the Week 52 visit and have both 6MWD and FVC assessments at the Week 52 visit (including make-up assessments or delayed visits). Subjects who completed the Week 52 visit and were able to do only 1 6MWT (instead of 2) at Week 52 will still be considered as completers. This population will be used for subject accounting purposes.

A subject who withdraws/discontinues from the study and returns for the end of study or early termination visit is not a completer and does not belong in the Completers population.

6.1.8. PK Population

The PK population consists of those randomized subjects who have been exposed to at least 1 dose of the study drug (ATB200/AT2221 or alglucosidase alfa/placebo) and have at least 1 PK assessment. For ERT-naïve subjects who undergo serial PK sampling, noncompartmental PK analysis is described in Section 3.3.5.2. For all other subjects who undergo sparse PK sampling, population PK analysis will be described in a separate Modeling and Simulation Plan.

6.2. Derived and Transformed Data

6.2.1. Study Day

The study has no Study Day 0. The date of first dose of study drug (First Dose Date) is labeled as “Day 1” for analysis purposes; it will serve as the reference start date.

Total duration of treatment will be calculated as the difference between the dates of last and first dose of study drug plus 1.

If the date of interest occurs on or after the first dose/randomization date, then study day will be calculated as (date of interest – date of first dose) + 1. If the date of interest occurs prior to the first dose/randomization date, then study day will be calculated as (date of interest – date of first dose).

6.2.2. Baseline Definition

In general, baseline is defined as the last non-missing measurement prior to the administration of the first dose of study drug, unless otherwise specified. It is understood that baseline may be different for different efficacy and safety endpoints.

- For the 6MWD, FVC, and SVC, the average of the last 2 values obtained on or prior to the first dose date will be used as the baseline value.
- For other functional assessments (such as the MMT, QMT, TUG, GSGC, PROMIS instruments, EQ-5D-5L (quantitative EQ-VAS score and descriptive health status), and R-PAct scale), the screening results will serve as the baseline values.
- For all other pulmonary function tests (MIP, MEP, and SNIP), baseline will be the last available value obtained on or prior to the first dose date.
- For safety data (including all lab assessments, physical examinations, ECG, vital signs, weight, etc), the last available result on or prior to the first dose date will be used as the baseline value (without considering the time of assessment on Day 1). If this value is missing, then the screening value will be used instead.

